All subjects aged 12 years and older, with at least 365 days of data availability before index date (ID) [ID defined as the date of the latest vaccine dose administered] AND data availability from 12/2020 onwards (i.e. the time when the roll-out of the vaccination campaign started) in the respective database will be included.

	Phase II C3-002 – Study Protocol							
	Author(s): [name], [name], [name]				Version: v2.1			
	Dissemination level: Public							

All studies will be carried out comparing the following cohorts, which we defined based on varying degrees of vaccine exposure and period of predominant SARS-CoV-2 variant as shown in Table 1 below.

COVID-19 vaccination history	Cohort number							
	1	2	3	4	5	6	7	8
1 dose only					x			
Complete primary vaccination course (monovalent only)	x	x	x	x		x	x	x
3rd dose, also called 1st booster (monovalent or any of the adapted, bivalent)	x	x	x	x			x	x
4th dose, also called 2nd booster (monovalent or any of the adapted, bivalent)		x						x
4th dose, also called 2nd booster (any of the monovalent)			x					
4th dose, also called 2nd booster (any of the adapted, bivalent boosters)				x				
Study period								
Start of roll-out 4 th dose/2 nd booster onwards	x	x	x	x				
XBB variant or later dominant	x	x	x	x				
Any variant dominant					x	x	x	x

*Cohorts 3 and 4 will only be created for databases where the vaccine product is reliably recorded in addition to vaccine brand.

Outcomes 1-2 will be assessed in cohorts 1-2 (and 3-4 where available), outcomes 3-7 will be assessed in cohorts 5-8.

Unvaccinated groups will not be used as a comparator in our study for vaccine effectiveness research because they may be very different from vaccinated individuals regarding their risk of infection with SARS-Cov-2. This study therefore focusses on the association of varying degrees of vaccine exposure and COVID-19 related outcomes.

Study period:

Period of “start of roll-out 4th dose/2nd booster dose onwards”: from 01/08/2022 - last available data for each database.

Period of “XBB variant or later dominant”: 01/03/2023 - last available data for each database. Note: This period is not covered by any of the data cuts onboarded for DARWIN EU at the time of protocol submission.

Period of “any variant dominant”: 01/01/2021 (when the wider roll-out of the vaccination campaign started) - last available data for each database.

Statistical analyses:

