Large-scale propensity scores (PS) will be computed to estimate the probability of receiving a 4th vaccine dose. Covariates to be included in the large-scale PS will be selected from co-medications and comorbidities recorded prior to cohort-specific index dates. Among those, covariates with a prevalence below 0.5% in the study population will be omitted. Logistic regression with LASSO regularization will then be used for variable selection. The list of selected covariates will be manually screened by 2 epidemiologists/clinical domain experts to exclude potential instrumental variables.

With matching, non-boostered counterparts will be assigned the date of when the boostered counterpart received their 4th vaccine dose as their “final” index date (index date for the matched pair).

In the matched cohorts, people will be followed up from their index date until the earliest of

- End of their observation (i.e. date of data extraction, death)
- next vaccine dose (4th vaccine dose for non-boostered group, 5th vaccine dose for boostered group)
- COVID-19 related hospitalization or death

	Phase II C3-002 – Study Protocol	
	Author(s): [name], [name], [name]	Version: v2.1
		Dissemination level: Public

Follow-up will be censored for the matched pair if one counterpart is censored, but not if one counterpart experiences the outcome.

The same procedure will be conducted in the calendar week after, with previously non-boostered people being allowed to be included in the booster cohort once they change exposure status. Non-boostered people can only be matched once to a booster counterpart during the whole study.

All booster and matched non-boostered people from sequential weekly matching will be combined into the exposed and unexposed cohort for subsequent analyses.

Outcomes:

- COVID-19 related hospitalization will be assessed for SIDIAP and ICPI.
- COVID-19 related death will be assessed for CPRD, IPCI and SIDIAP.

Vaccine effectiveness analyses:

Cox proportions hazard models will be used to calculate hazard ratios (HR) for the outcomes of COVID-19 related hospitalisation and COVID-19 related death.

Negative control outcomes and empirical calibration for HR will be used as an additional measure to measure and minimise any potential residual confounding.

Kaplan-Meier plots and/or cumulative incidence plots will be used to illustrate survival analyses.

Vaccine effect waning:

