Large-scale propensity scores (PS) will be computed to estimate the probability of receiving a 4th vaccine dose. Covariates to be included in the large-scale PS will be selected from co-medications and comorbidities recorded prior to cohort-specific index dates. Among those, covariates with a prevalence below 0.5% in the study population will be omitted. Logistic regression with LASSO regularization will then be used for variable selection. The list of selected covariates will be manually screened by 2 epidemiologists/clinical domain experts to exclude potential instrumental variables.

The same procedure will be conducted in the calendar week after, with previously non-boostered people being allowed to be included in the booster cohort once they change exposure status. Non-boostered people can only be matched once to a booster counterpart during the whole study. With matching, non-boostered counterparts will be assigned the date of when the booster counterpart received their 4th vaccine dose as their “final” index date (index date for the matched pair).

All booster and matched non-boostered people from sequential weekly matching will be combined into the booster and non-boostered cohort for subsequent analyses. The study inclusion and sequential matching process is illustrated in [Figure 8.8.3.1](#) below.

[figure not shown]

	Phase II C3-002 – Study Protocol	
	Author(s): [name], [name], [name]	Version: v2.1
	Dissemination level: Public	

Figure 8.8.3.1 Study inclusion and sequential matching process

	Phase II C3-002 – Study Protocol	
	Author(s): [name], [name], [name]	Version: v2.1
		Dissemination level: Public

Follow-up

In the matched cohorts, people will be followed up from their index date until the earliest of

- End of their observation (i.e. date of data extraction, death)
- 2nd booster vaccination for unvaccinated group, 3rd booster for vaccinated group etc.
- COVID-19 related hospitalization or death, with outcome date being defined as the date of first COVID-19 diagnosis/positive test related to hospitalization or death.

Follow-up will be censored for the matched pair if one counterpart is censored, but not if one counterpart experiences the outcome.

Outcomes

The outcomes are defined in detail in section 8.6.2.

COVID-19 related hospitalization will be assessed for SIDIAP and IPCI. COVID-19 related death will be assessed for CPRD, IPCI and SIDIAP.

Statistical Analyses

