Objective 1: Vaccine effectiveness

Cox proportions hazard models will be used to calculate hazard ratios (HR) for the outcomes of COVID-19 related hospitalisation and COVID-19 related death.

Negative control outcomes will be used as an additional measure to measure any potential residual confounding. NCO are outcomes not causally associated with the exposure of interest²⁶, here COVID-19 vaccination. However, their association with vaccination is ideally impacted by the same type of unmeasured confounding, e.g. healthcare-seeking behavior, as the vaccination-outcome association²⁷. In the scenario of potential unmeasured confounding being detected by NCO, empirical calibration²⁵ for HR might be considered to minimise bias.

Vaccine effectiveness will be calculated as $1 - HR$. Kaplan Meier plots and/or cumulative incidence plots will be used to illustrate survival analyses.

The proportional hazard assumption will be tested visual investigation of log(-log) plots. In the scenario of substantial violation of the proportional hazard assumptions, alternative models/model adaptations will be used.

Objective 2: Waning of vaccine effectiveness

Hazard ratios will be calculated for subsequent time windows after index date, i.e. in bi-weekly intervals. Monthly intervals will be used in case of small event counts to increase sample size and power if needed. Vaccine effectiveness will be calculated as $1 - HR$.

Kaplan Meier plots and/or cumulative incidence plots will be used to illustrate survival analyses.

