
11. LIMITATIONS OF THE RESEARCH METHODS

General limitations:

- The study will be informed by routinely collected health care data and so data quality issues must be considered.
- We will use large-scale propensity scores to minimize measured confounding, and NCOs to assess potential residual confounding. However, given the observational nature of our data, we cannot rule out remaining confounding, which could partially account for findings in this study.

Study-specific limitations:

- Mandatory PCR test for people who tested positive in lateral flow home tests were skipped in early 2022. As not all positive home tests were reported and recorded as clinical diagnoses in primary care databases, it is likely that non-severe SARS-CoV-2 infections are underreported after 02/2022. Moreover, underreporting of COVID-19 for asymptomatic case is to be expected. Underreporting of COVID-19 could lead to misclassification of outcomes for Objectives 4-6, namely post-acute COVID-19 complications (diabetes, cardiac events). For objectives 4-6, we require a minimum follow-up time of 12months after SARS-CoV-2 to identify cases of new-onset diabetes and/or cardiovascular complications. With this, only infections recorded before 02/2022 will be included in the study.
- Routine screening has been impacted by the pandemic, and therefore diagnoses of new conditions, e.g. T2DM might have been delayed depending on testing practices.
- COVID-19 related hospitalization is unlikely to be underreported as people are likely to be asked about previous SARS-CoV-2 infections at hospital admission (Objective 3). However, positive COVID-19 test results that occur around hospitalization do not constitute a hospitalization *due to* COVID-19.

	Phase II C3-002 – Study Protocol	
	Author(s): [name], [name], [name]	Version: v2.1
		Dissemination level: Public

We will use the data cuts currently onboarded for DARWIN EU for CPRD, IPCI and SIDIAP. However, none of those is currently covering the period of XBB variant predominance. We therefore designed the study to assess objectives 1 and 2 to start at the time the 4th vaccine doses were made available for people.

MANAGEMENT AND REPORTING OF ADVERSE EVENTS/ADVERSE REACTIONS

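### Objective 2 ties no negative control to its time windows, so a change in residual confounding after the dose could pass for waning or hide it

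*Protocol*

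**What the plan says.** Protocol section 8.8.3, under Objective 2, gives the whole waning analysis: "Hazard ratios will be calculated for subsequent time windows after index date, i.e. in bi-weekly intervals". The fallback is: "Monthly intervals will be used in case of small event counts to increase sample size and power if needed". VE is 1 - HR, and survival or cumulative incidence plots are added. The abstract's paragraph on waning is the same in substance. Neither mentions a negative control.

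Under Objective 1, the same section says: "Negative control outcomes will be used as an additional measure to measure any potential residual confounding". If the NCOs suggest unmeasured confounding, empirical calibration "for HR might be considered to minimise bias". The abstract is firmer: "Negative control outcomes and empirical calibration for HR will be used as an additional measure to measure and minimise any potential residual confounding". That sentence stands under vaccine effectiveness analyses, before the separate subheading for waning. Sections 8.8.4 and 8.8.5 write NCOs into Objective 3 and Objectives 4-6.

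Section 11 adds a study-wide statement: "We will use large-scale propensity scores to minimize measured confounding, and NCOs to assess potential residual confounding". It names no time windows.

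Three other provisions bear on the point:
- Follow-up starts at the index date (section 8.4).
- Pairs are censored together: "Follow-up will be censored for the matched pair if one counterpart is censored, but not if one counterpart experiences the outcome" (section 8.8.3).
- No sensitivity analyses are planned (section 8.8.6).

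**The concern.** Objective 1 asks for a level of VE; Objective 2 asks for a trend. A bias that is constant over follow-up puts the level wrong but leaves the trend on the log-HR scale intact. A bias that changes with time since the dose enters the trend directly and has the same form as a real change in protection.

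The design leaves room for such a change. Follow-up begins on the day of the dose with no lag, so the first window covers the days when unrecorded acute illness or frailty would most plausibly have led someone to defer a dose. A comparator's own fourth dose later ends the pair, so the pairs still at risk in late windows are those whose comparator stayed unboosted. Either feature could shift residual confounding between early and late windows, in either direction.

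The protocol accepts that unmeasured confounding may remain and chooses NCOs to look for it. For the one objective whose result is a time pattern, the stated analysis gives no means of telling a change in protection from a change in bias. A regulator could conclude that protection declines when it does not, or miss a decline that is real.

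**Working it through.** The protocol states no sample size, event count or expected HR for Objective 2, so there is no figure of its own to reproduce. What follows illustrates the mechanism. **All bias values are assumptions.**

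**Model.** In window w, observed HR = true HR x b(w), and VE = 1 - observed HR. The true HR is held at 0.50, so there is no waning.

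**Step 1: bias that fades.**

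| Assumed bias, first to last window | First-window VE | Last-window VE | False fall |
|---|---|---|---|
| 0.60 to 0.95 | 1 - 0.50 x 0.60 = 70.0% | 1 - 0.50 x 0.95 = 52.5% | 17.5 points |
| 0.85 to 0.97 | 1 - 0.50 x 0.85 = 57.5% | 1 - 0.50 x 0.97 = 51.5% | 6.0 points |

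**Step 2: one overall calibration factor.** Take the geometric mean of the two biases as the overall NCO estimate.
- Stronger case: sqrt(0.60 x 0.95) = 0.755. Calibrated VE is 1 - 0.300/0.755 = 60.3%, then 1 - 0.475/0.755 = 37.1%.
- Milder case: sqrt(0.85 x 0.97) = 0.908. Calibrated VE is 1 - 0.425/0.908 = 53.2%, then 1 - 0.485/0.908 = 46.6%.

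The false fall remains. Dividing every window by one constant leaves the drift in log HR unchanged: ln(0.95/0.60) = 0.46 and ln(0.97/0.85) = 0.13, before and after.

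**Step 3: window-specific control.** If the NCOs carry the same bias as the outcome in each window, dividing each window's HR by its own NCO HR returns 0.50 throughout.

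**Step 4: the opposite direction.** Reverse the milder case, so that the bias runs from 0.97 to 0.85. A true HR rising from 0.50 to 0.50 x 0.97/0.85 = 0.571 (true VE 50% to 42.9%) is then observed as 0.50 x 0.97 = 0.485 and 0.571 x 0.85 = 0.485. VE appears flat at 51.5%, and the real waning is hidden.

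**Step 5: smooth fade as a cross-check.** Let b(t) = b0^(0.5^(t/h)) with half-life h = 4 weeks, over 13 two-week windows with midpoints at 1 to 25 weeks and true VE 50%.
- b0 = 0.85: VE 56.4% to 50.1%, a fall of 6.3 points.
- b0 = 0.7: VE 63.0% to 50.2%, a fall of 12.7 points (from unrounded values). The NCO HR runs from 0.74 to 1.00, but its overall value is 0.93. Calibrating by 0.93 still gives 60.0% falling to 46.2%.
- b0 = 0.5: VE 72.1% to 50.5%, a fall of 21.6 points.
- Constant bias of 0.7: VE is 1 - 0.50 x 0.7 = 65% in every window, with the level wrong and no trend.

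**Step 6: precision of a per-window NCO.** With 1:1 matching, two-sided 0.05 and 80% power, events needed = 4 x (1.960 + 0.842)^2 / (ln HR)^2 = 31.4 / (ln HR)^2. This gives 66 events for an NCO HR of 0.5, 247 for 0.7 and 1,189 for 0.85.

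**The case against.** **The controls already in the plan may leave little bias.** The large-scale propensity score uses conditions and medications from the 30 days before index as well as longer look-backs (section 8.6.3). Pairs are matched on age, sex, location, prioritisation conditions, immunocompromised status and time since the last dose. Anyone with COVID-19 recorded in the previous 90 days is excluded (section 8.8.3). This stands: recent illness is addressed where it is recorded, and the documents do not show that a time-varying bias survives.

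**Section 11 commits to NCOs across the study, and whether they run overall or by window could be settled in a SAP.** This stands in part. The list and coding of NCOs can wait, and nothing prevents a SAP from adding windows. But the protocol fixes the Objective 2 analysis, writes NCOs by name into every other objective, and plans no sensitivity analysis that would fill the gap.

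**Readings that go too far.**
- A reader might infer that a fading healthy-vaccinee bias will be reported as waning. The documents establish neither its presence nor its direction; a growing bias would hide waning instead.
- A reader might take the abstract's remark about people excluded "because they may be very different from vaccinated individuals regarding their risk of infection with SARS-Cov-2" to mean that the protocol regards those who decline a booster as non-comparable. The remark concerns unvaccinated people. The Objective 2 comparators have three doses and were chosen deliberately.
- A reader might expect per-window NCOs to cure selection from pair censoring. That is a separate issue, and NCOs help only so far as they share the same time-varying bias.

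**Conclusion.** The concern holds in conditional form. As written, Objective 2 cannot distinguish a change in vaccine protection from a change in residual confounding with time since the dose, and a single overall NCO estimate or calibration factor would not help. The error could run in either direction.

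The size is unknown. With a constant true HR of 0.50 and assumed biases of 0.85 to 0.97 and 0.60 to 0.95, false waning is about 6 to 18 VE points. The smooth-fade model gives the same order. Across true VE of 30% to 67.8% and half-lives of 4 or 8 weeks, it gives 4 to 30 points. These are scenarios, not predictions. A bias that stays constant would create no trend. The change is worth making because the NCOs are already planned and only their use by window is missing.

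**What to change.** In section 8.8.3, Objective 2, add the following:
- Estimate the planned NCO HRs in the same windows and on the same matched pairs as the outcome HRs, pooled across NCOs, with monthly windows where counts are small.
- Report the NCO HR beside the outcome HR for each window.
- Interpret any decline in VE in light of any trend in the NCO HRs.
- If empirical calibration is used for Objective 2, perform it per window. The abstract and section 8.8.3 should also agree on whether calibration is planned or optional.

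Two additions are better avoided. A strict rule that waning is declared only if it persists after dividing by the NCO HR would add NCO noise to every window and could hide real waning when events are sparse. Non-COVID-19 death is a doubtful control. It is not listed in Table 8.6.2.1, and COVID-19 related death requires a recorded diagnosis or test within 28 days. Section 11 expects non-severe infections to be underreported after 02/2022, so unrecorded COVID-19 deaths could enter the control.

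The cost is protocol or SAP wording and a further run of analyses on NCOs already intended. The main downside is precision: at about 247 events per window for an NCO HR of 0.7 and 1,189 for 0.85, a flat NCO series based on few events should not be read as absence of bias.

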8.8.4 Objective 3: Vaccine effectiveness to prevent COVID-19 related mortality

Objective 3 will assess vaccine effectiveness to prevent all-cause mortality in the 3 months/6 months after discharge from a COVID-19 hospitalisation. This objective will be assessed for SIDIAP and IPCI only, as no information on hospitalisation are available in CPRD.

	Phase II C3-002 – Study Protocol	
	Author(s): [name], [name], [name]	Version: v2.1
		Dissemination level: Public

The following comparisons will be conducted:

- 1st dose vaccinated vs. 2nd dose vaccinated [cohort 5 vs. 6]
- 2nd vaccinated vs. 3rd dose vaccinated [cohort 6 vs. 7]
- 3rd dose vaccinated vs. 4th dose vaccinated [cohort 7 vs. 8]

Study population

The study populations will be derived similar to the inclusion process outlined for objectives 1-2 above, including sequential matching. The following inclusion criteria will be applied:

- At least 365 days of data availability in the respective database
- At least 90days of time elapsed since the previous vaccine dose for the 3rd or 4th vaccine dose
- At least 21days of time elapsed since the previous vaccine dose for the 2nd vaccine dose
- At least 90days of time elapsed since the last record of a clinical diagnosis of COVID-19 or positive SARS-COV-2 test.

Outcomes

For contextualization, we will assess vaccine effectiveness to prevent COVID-19 hospitalization for the mentioned comparisons. The primary study outcome will be COVID-19 hospitalization followed by death within 3 or 6 months from discharge.

Statistical Analyses

Vaccine effectiveness analyses for COVID-19 related mortality following hospital discharge:

Incidence rates will be calculated for the matched cohorts and both outcomes. Cox proportional hazard models will be calculated for each outcome to provide HR. Follow-up will start at index date, i.e. the date of vaccination with respective new dose for matched pairs.

Negative control outcomes will be used as an additional measure to measure potential residual confounding. In the scenario of potential unmeasured confounding being detected by NCO, empirical calibration²⁵ for HR might be considered to minimise bias.

Kaplan Meier plots and/or cumulative incidence plots will be used to illustrate survival analyses.

8.8.5 Objectives 4-6: Vaccine effectiveness to prevent post-acute COVID-19 complications

Objectives 4-6 evaluate vaccine effectiveness to prevent post-acute COVID-19 complications, namely new onset diabetes and cardiovascular complications, and will be conducted in all 3 databases.

Similar to objective 3, we will compare people with 1st dose vaccination vs. 2nd dose vaccination [cohort 5 vs. 6], 2nd dose vaccination vs. 3rd dose vaccination [cohort 6 vs. 7] and 3rd dose vaccination vs. 4th dose vaccination [cohort 7 vs. 8].

Study population

The study populations will be derived similar to the inclusion process outlined for objectives 1-3 above, including sequential matching. Inclusion criteria will be applied as outline in section 8.8.4 for Objective 3.

For objectives 4 and 5, people with the respective outcomes of interest, i.e. diabetes recorded anytime before their index date will be excluded for the respective objective. For objective 6, an outcome-free washout window of 365days prior to index date will be implemented.

	Phase II C3-002 – Study Protocol	
	Author(s): [name], [name], [name]	Version: v2.1
		Dissemination level: Public

We will require at least 12 months of follow-up after SARS-CoV-2 infection to assess post-acute complications for outcomes 5, 6, and 7. If people die within 12 months after COVID-19 they will contribute patient-time until death to the analyses. Only infections recorded 12 months before the end of data availability will be included.

Outcomes

- SARS-CoV-2 infection [for contextualization]
- SARS-CoV-2 infection + New onset diabetes Type 1 diabetes within 30-365 days after COVID-19
- SARS-CoV-2 infection + New onset diabetes Type 2 diabetes within 30-365 days after COVID-19
- SARS-CoV-2 infection + cardiovascular events (cerebrovascular disorders, dysrhythmias, ischemic and non-ischemic heart disease, pericarditis, myocarditis, heart failure and thromboembolic disease) in the 12 months after a SARS-CoV-2 infection

Vaccine effectiveness analyses for post-acute COVID-19 complications:

Incidence rates will be calculated for the matched cohorts and for each outcome. Cox proportional hazard models will be calculated for each outcome to provide HR. Follow-up will start at index date, i.e. the date of vaccination with respective new dose for matched pairs. As previous research showed, no relevant difference in effect estimates was seen for post-COVID-19 symptoms when used fine-grey models accounting for death as competing risk compared to Cox regression². We therefore will not account for competing risk in this analysis.

Negative control outcomes and will be used as an additional measure to measure any potential residual confounding. A list of NCOs used in previous vaccine safety and effectiveness studies will be used. In the scenario of potential unmeasured confounding being detected by NCO, empirical calibration²⁵ for HR might be considered to minimise bias.

Kaplan-Meier plots and/or cumulative incidence plots will be used to illustrate survival analyses.

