Time (when follow up begins and ends):	Follow-up start: at index date of matched single-vaccinated/ double-vaccinated people [double-vaccinated vs. triple vaccinated; triple vaccinated vs. 4 th dose vaccinated] after start of roll-out of vaccination programs i.e. from 01/01/2021 End of follow-up: End of their observation (i.e. date of data extraction, database availability or death), next vaccine dose or outcome event, whatever comes first.
Setting:	Primary care electronic health records from SIDIAP [Spain], IPCI [The Netherlands] and CPRD GOLD [UK]
Main measure of effect:	
 • Incidence rate for outcomes-100'000 person-years • Vaccine effectiveness against post- acute COVID-19 complications, calculated as 1 - HR

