8.4 Follow-up

For all analyses, follow-up time will start from index date.

End of follow-up for each objective will be the end of a person’s observation time (i.e. date of data extraction, database availability or death), the date of their next vaccine dose, fixed duration or the date of the respective outcome event, whatever comes first

Table 8.4.1: Operational Definition of Time 0 (index date) and other primary time anchors

Study population name(s)	Time Anchor Description (e.g. time 0)	Number of entries	Type of entry	Washout window	Care Setting ¹	Code Type	Diagnosis position	Incident with respect to...	Measurement characteristics/ validation	Source of algorithm
1 dose only	Vaccination date 1 st dose	1	incident	All history	OP	RxNorm	n/a	vaccination	n/a	n/a
Complete primary vaccination course (2 doses)	Vaccination date 2 nd dose	1	n/a	21days	OP	RxNorm	n/a	n/a	n/a	n/a
3rd dose (monovalent or adapted/bivalent)	Vaccination date 3 rd dose	1	n/a	90days	OP	RxNorm	n/a	n/a	n/a	n/a
4th dose (monovalent or adapted/bivalent)	Vaccination date 4 th dose	1	n/a	90days	OP	RxNorm	n/a	n/a	n/a	n/a
4th dose (any monovalent)	Vaccination date 4 th dose	1	n/a	90days	OP	RxNorm	n/a	n/a	n/a	n/a
4th dose, (any adapted/bivalent boosters)	Vaccination date 4 th dose	1	n/a	90days	OP	RxNorm	n/a	n/a	n/a	n/a

OP = outpatient, n/a = not applicable

	Phase II C3-002 – Study Protocol	
	Author(s): [name], [name], [name]	Version: v2
		Dissemination level: Public

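### Objectives 4-6: the 12-month follow-up minimum after infection conflicts with ending follow-up at the next dose, selects infected people on later events, and leaves uninfected person-time that cannot produce an event

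*Protocol*

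**What the plan says.** Objectives 4-6 concern type 1 diabetes, type 2 diabetes and cardiovascular events after SARS-CoV-2 infection (outcomes 5-7, all listed as primary in section 8.6.2).

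- **Minimum follow-up.** Section 8.8.5: "We will require at least 12 months of follow-up after SARS-CoV-2 infection to assess post-acute complications for outcomes 5, 6, and 7". The only exemption is "If people die within 12 months after COVID-19 they will contribute patient-time until death to the analyses". Leaving the database and taking another dose are not exempted.
- **Calendar limit.** The same paragraph adds "Only infections recorded 12 months before the end of data availability will be included".
- **Time zero.** Section 8.8.5: "Follow-up will start at index date, i.e. the date of vaccination with respective new dose for matched pairs". It is not the infection date.
- **End of follow-up.** Table 7.1C stops at end of observation, "next vaccine dose or outcome event, whatever comes first". Section 8.4, which covers every objective, lists "the date of their next vaccine dose, fixed duration or the date of the respective outcome event, whatever comes first". No fixed duration is defined for these objectives.
- **Pair censoring.** Section 8.8.3, written for objectives 1-2: "Follow-up will be censored for the matched pair if one counterpart is censored, but not if one counterpart experiences the outcome". Section 8.8.5 connects to it only through "The study populations will be derived similar to the inclusion process outlined for objectives 1-3 above, including sequential matching".
- **Event dating.** Section 8.8.3 dates a severe outcome at the related COVID-19 diagnosis or positive test. Section 8.8.5 gives no dating rule.
- **Sensitivity analyses.** Section 8.8.6 plans none.

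**The concern.** One rule demands a year of follow-up after infection. Another stops follow-up at the next dose, which can come well before that year is over. Two programmers could build materially different cohorts from this text.

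The minimum also applies only after an infection, so an infected person's place in the analysis depends on what happens later. Infection is the event vaccination is meant to affect, so the exclusion could differ between dose groups. An uninfected person faces no such requirement.

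Finally, infections late in the data are barred as events, but nothing stops uninfected people from continuing to add person-time over the same months. Incidence per 100,000 person-years is a stated main measure in Table 7.1C, and its denominator then contains time that by rule cannot lead to an event.

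**Working it through.** The protocol states no sample size or event count for these objectives, so there is no figure to reproduce.

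**1. Can both rules hold?** Let L be the number of days from index dose to next dose, and let infection occur U days after the index dose. Follow-up after infection is at most L − U. If L is 365 or less and U is above 0, then L − U is below 365 and the 12-month minimum fails. This needs no assumption about dosing patterns. Section 8.8.4, which section 8.8.5 adopts, allows a second dose from 21 days and a third or fourth from 90 days. These are eligibility minimums, not observed intervals, but they show that L below 365 is admitted.

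**2. Time in which a new infection cannot count.** Table 8.2.1 gives data locks by month; month-ends are assumed. The study period starts on 01/01/2021.

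- SIDIAP, lock 06/2022: 545 days; 365/545 = 67%.
- IPCI, lock 12/2022: 729 days; 365/729 = 50%.
- CPRD GOLD, lock 01/2023: 760 days; 365/760 = 48%.

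The last eligible infections are therefore at about 06/2021, 12/2021 and 01/2022. Section 11 agrees, saying that only infections before 02/2022 will enter. People infected before the cut-off can still have a complication in the last 12 months; people uninfected at the cut-off cannot become cases. These are shares of calendar time. The share of person-time depends on dose dates, which are not given.

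**3. How much of the 30-365-day window falls before the next dose?** Assume that everyone takes a next dose after L days, that infection is uniform on (0, L), and that follow-up stops at that dose. The window is 335 days long. For L from 30 to 365 the average share seen is (L − 30)² / (2 × 335 × L):

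- L = 90: 60² / (670 × 90) = 3,600/60,300 = 6%.
- L = 180: 150² / (670 × 180) = 22,500/120,600 = 19%.
- L = 270: 240² / (670 × 270) = 57,600/180,900 = 32%.

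For L of 365 or more the share is (L − 197.5)/L, which reaches 50% at L = 395 and 73% at L = 730.

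**4. Allowing for people who never take another dose.** Let a proportion p take no further dose and keep the full window, with L = 180 for the rest (share 0.187). Individual censoring gives p + (1 − p) × 0.187. Pair censoring, with the two members independent, gives p² + (1 − p²) × 0.187.

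- p = 0.2: 35% individual, 22% pair.
- p = 0.5: 0.5 + 0.5 × 0.187 = 59% individual; 0.25 + 0.75 × 0.187 = 39% pair.
- p = 0.8: 84% individual, 71% pair.

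The protocol gives neither L nor p, so the loss could be most of the window or a small part of it.

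**The case against.** A reader might infer that most complications cannot be observed. The documents do not support that. It holds on average if everyone is re-dosed in under about 395 days, and fails if many people take no further dose. A reader might also take pair censoring as given. It is written for objectives 1-2 only; the link in section 8.8.5 names inclusion and matching, so for objectives 4-6 it is at most implied.

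There is also a coherent reading in which the observability problem disappears. The outcomes are composites of infection plus complication. If the event were dated at infection, as section 8.8.3 does for severe outcomes, a later dose would not censor it, and the 12 months would be the look-ahead needed to classify the infection. The protocol does not say this for objectives 4-6, and letting those who die contribute time until death sits awkwardly with it. Even so, excluding infected people who leave within the year, and the unmatched uninfected time, would remain.

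The minimum can also be read as a calendar cut-off only, as section 11 partly does. That would remove much of the selection. But the calendar limit has its own sentence, so the requirement before it appears to add something.

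Lastly, matched members share an index date, so time that cannot yield events falls similarly on both groups. That stands: dilution of the incidence rates follows from the rules, but a bias in the hazard ratio of known direction or size has not been shown.

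**Conclusion.** The conflict is real and rests on the protocol's own text: individual censoring at the next dose is explicit, so it needs no pair censoring. Read literally, the minimum conditions on staying observed, and not re-vaccinated, for a year after infection, and does so for infected people only. The size of that selection cannot be derived from the document.

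The denominator problem follows from the stated locks and the 12-month rule: about 67% of the study period in SIDIAP and 50% and 48% in IPCI and CPRD lie after the last eligible infection, with no stated stop for uninfected person-time. The incidence rates are diluted, to a degree that depends on when doses were given.

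The loss of complications to next-dose censoring is conditional. It rests on unstated dosing intervals, the share never re-dosed, whether pair censoring applies, and how events are dated. With no sensitivity analysis planned, the results would not reveal it.

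**What to change.** In sections 8.8.5 and 8.4 and Table 7.1C, with the abstract brought into line:

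- **(a)** Replace the 12-month minimum with censoring of infected people at end of observation.
- **(b)** If an infection cut-off date is kept, for instance because section 11 expects under-recording of infections after 02/2022, stop uninfected person-time at that same date in both dose groups.
- **(c)** State one reconciled rule for event dating and for next-dose censoring after infection, say whether pair censoring applies, and define or delete the fixed duration in section 8.4. Report the alternative handling of doses given after infection as a sensitivity analysis.

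Whether to follow people past a later dose is a trade-off, not a correction. It changes the estimand, because a comparator may then have received the dose under study. That is why (c) asks for a stated choice plus the alternative.

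The cost is protocol wording and some extra cohort programming; no new data are needed. Some infected people will contribute less than 12 months, which a time-to-event analysis can accommodate.
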